#### 8.5 Multi-centre Studies

IPCAS is a multi-centre trial, comprising multiple GP practices. The trial uses a two-level cluster randomised design, with GP practices representing the clusters, and patients nested within GP practice. GP practice is the unit of randomisation. The data will be analysed to reflect the hierarchical nature of the study design using mixed effect models.

#### 8.6 Multiple Testing

This study has two co-primary outcomes: (emotion and handicap subscales of the SIS). The Holm-Bonferroni procedure (Holm, 1979) will be used to handle the co-primary endpoints and issue of multiplicity. 97.5% Cls for the two primary outcomes will be reported as a conservative measure.

Confidence intervals for secondary and exploratory outcomes will be reported at the 95% level.

# 9 Summary of Study Data

Summary data will be provided for a variety of study data via tables and/or graphs as outlined in *IPCAS SAP V1.0\_23April2020 figures and tables listing.xlsx*.

Where results are presented as summary statistics, continuous variables will be summarised using the following descriptive statistics:

- n (the non-missing sample size)
- mean
- standard deviation
- median
- 25th percentile
- 75th percentile
- maximum
- minimum.

Where results are presented as summary statistics, categorical variables will be summarised using frequency and percentages (based on the non-missing sample size) of all observed levels. Non-observed levels should also be included if they form part of an expected set of category levels (e.g. from a categorical questionnaire question with a finite set of response options).

In general, summary statistics will be presented in tables by treatment and by gender, with a column for each treatment group or gender. If appropriate, a table may also be split by questionnaire number (baseline, 3 months, 6 months, etc). For study data that is summarised in a more raw form and without the need for summary statistics (e.g. recruitment, withdrawals, SAEs, etc), data will be presented in a table or graph as appropriate. The quantity of missing data will also be summarised for relevant outcomes, by treatment group, at 6months at also 12 months.

Descriptive statistics for Intervention fidelity will be presented as detailed in Section 6 (*IPCAS V1.0\_23April2020 figures and tables.docx.*)

# 9.1 Subject and Cluster Disposition

Summary data for subject disposition and an overview of the time-dependent rates of recruitment will be presented:

- Summary of cluster randomisation to treatment sequence (Table 1.1)
- Summary of time dependent rates of GP practice recruitment (Table 1.1 and Figure 1.1)
- Summary of time dependent rates of patient recruitment (Figure 1.2 and 1.3)
- Summary of patient flow (Table 2.1)
- Subject disposition CONSORT diagram (Figure 2.3)

Questionnaire date for each patient will be recorded at baseline, 6 and 12 months and return rates tabulated:

- Return rates for questionnaires at baseline, 6 and 12 months (Table 2.5).
- Data completeness for SIS emotional domain and SIS handicap domain at 12 months (the coprimary end-points) [where complete data is considered a binary variable for each subject at a given domain] (Table 2.6).

At each stage of the trial, the following variables will be recorded and define whether a patient reached that stage of the trial:

Questionnaire date (dd-mmm-yyyy)

Patients without the above information will have missed a visit, been lost to follow-up or withdrawn due to one of the following:

- Death
- Health deterioration
- Taking part is too burdensome
- 2nd questionnaire not relevant
- 6m questionnaire not relevant
- Left the practice
- No reason given
- Intervention is not relevant
- Will not complete 12m questionnaire
- Not a stroke.

Summary tables of withdrawal will be presented (Tables 4.3 - 4.6).

Intervention progress will be summarised in the following figures and diagrams:

- Breakdown of stroke review progress per recruited intervention GP practice up to [date] (Table 2.2)
- Breakdown of MLAS interest per recruited intervention GP practice up to [date] (Table 2.3)
- Breakdown of the number of stroke survivors attending MLAS by area up to [date] (Table 2.4)
- Progress of enhanced stroke review completion at each intervention GP practice from May 2018 to end of study. GP practice in order of randomisation (Figure 2.1)
- Breakdown of MLAS progress by intervention site over the period May 2018 to [date] (Figure 2.2)

Data concerning the intervention care model will be collected under the following:

- 1) Training
- 2) Enhanced Stroke Review
- 3) MLAS

Process data, fidelity of delivery and receipt will be discussed in Section 10.2.1.

Data concerning usual care will be collected from control GP practices either face-to-face, over the phone, or email correspondence with n (%) being reported for the following categories:

- 1) Frequency of reviews (annually, as needed, not reported)
- 2) Mode of review (face to face, combination)
- 3) Healthcare professional(s) involved in review (GP-led, nurse-led, HCA-led, combination)
- 4) Type of review (stroke-specific, multi-morbidity, other)
- 5) Review content (Quality and Outcomes Framework-related, other)

Descriptive statistics for the Intervention and usual care models will be presented as detailed in Section 6 (IPCAS V0.7\_28JAN2020 figures and tables.docx.)

#### 9.2 Derived variables

There are several derived variables in the IPCAS trial, primarily relating to the questionnaire data. The derived variables and how they are calculated are detailed below.

#### 9.2.1 SIS domain total scores

The SIS questionnaire has 8 domains, and each domain contains a series of questions which are each scored on a scale of 1-5. A total score for each domain can be calculated and then transformed onto a standardised scale of 0-100 for each individual.

Three questions within the SIS emotional domain (domain 3) are reverse scored (3f, 3h and 3i). For the three reverse scored questions, these are back-transformed using the following equation:

(x + 1) - y

Where x=maximum possible score and y=raw score.

For example, for an SIS 3h score of 4, this would be back-transformed to:

For each domain, the total raw score is calculated as the sum of the raw scores, using the backtransformed scores in place of the "raw" reverse scores in the case of 3f, 3h and 3i. For example, for the emotional domain the total raw score for each individual is the sum of SIS 3a, 3b, 3c, 3d, 3e and 3g, and the back-transformed scores for 3f, 3h and 3i.

The domain total score can then be calculated on a standardised scale of 0-100 for each individual:

Standardised domain total score = [(total raw score for domain-lowest possible raw score for domain)/possible raw score range for domain]\*100

For example, for the emotional domain (domain 3), the lowest possible raw score is 9 (a score of 1 for all 9 questions in domain 3), and the possible raw score range is 45-9=36 (maximum possible score is 9x5=45, minimum possible score is 9x1=9).

#### 9.2.2 SIS-SF total score

The SIS-SF is made up of 8 questions, one from each domain of the full SIS questionnaire. It includes the following 8 questions only: 1c, 2f, 3d, 4b, 5h, 6f, 7e, 8b. Each question is scored on a scale of 1-5. A total score for SIS-SF can be calculated and then transformed onto a standardised scale of 0-100 for each individual. There are no reverse scored questions within the SIS-SF.

For SIS-SF total, the total raw score is calculated as the sum of the raw scores for the eight questions. The domain total score can then be calculated on a standardised scale of 0-100 for each individual:

Standardised SIS-SF total score = [(total raw score-lowest possible raw score)/possible raw score range]\*100

The lowest possible raw score is 8 (a score of 1 for all 8 questions in SIS-SF), and the possible raw score range is 40-8=32 (maximum possible score is 8x5=40, minimum possible score is 8x1=8).

Q9 is a visual analogue scale (VAS) score of perceived overall health which asks participants to indicate their overall health post-stroke ranging from 0 (No recovery) to 100 (Full recovery).

#### 9.2.3 EQ-5D-5L total score

The EQ-5D-5L questionnaire is made up of five questions, on:

- i) mobility
- ii) self-care
- iii) usual activities
- iv) pain & discomfort
- v) anxiety & depression

Each of the five questions is scored on a scale of 1-5, where:

- 1 indicates no problem
- 2 indicates slight problems
- 3 indicates moderate problems
- 4 indicates severe problems
- 5 indicates extreme problems

A "health state" score is given for each individual by writing the score for each of the five questions as a 5-digit number (in order of questions i-v). For example, if an individual scored 1 on mobility, 2 on self-care, 3 on usual activities, 4 on pain & discomfort, and 5 on anxiety & depression, their "health state" score would be written as 12345.

There are a total of 3125 possible different "health states", each represented by a 5 digit number. A health state of 11111 indicates no problems in any of the five dimensions measured, whereas a health state of 55555 indicates extreme problems in all of the five dimensions measured. These "health states" can be converted into a single index value for each individual using country-specific crosswalk value sets available along-side the EQ-5D-5L instrument.

For IPCAS, the UK crosswalk value set (see EQ-5D-5L\_Crosswalk\_Index\_Value\_Calculator.xls) will be used in the EQ-5D-5L total score calculations. The profile/health state is converted into a Country specific index value ranging from -0.594 (extreme problems across all health states) to 1 (no problems across all health states). The VAS score ranges from 0 (Worst health) to 100 (Best health imaginable).

The VAS score ranges from 0 (Worst health) to 100 (Best health imaginable).

#### 9.2.4 |CECAP-A total score

The ICECAP-A questionnaire is made up of five "questions", with each question assigned a score between 1 and 4. A score of 1 is given to a response reflecting the lowest quality of life, and a score of 4 is given to a response reflecting the maximum quality of life. For example, for question one, "Feeling settled and secure", the following scores would be assigned:

- I am unable to feel settled and secure in any areas of my life: score=1
- I am able to feel settled and secure in a few areas of my life: score=2
- I am able to feel settled and secure in all areas of my life: score=3
- I am able to feel settled and secure in all areas of my life: score=4

The scores assigned to the five questions within a patient are then written as five consecutives numbers to give an overall 5-digit score for each patient. An overall score of '44444' for a patient represents the maximum quality of life measured by the questionnaire, and a score of '11111' measures the minimum quality of life measured by the questionnaire. All five questions must be answered to assign an overall score.

These overall 5-digit scores are then translated into an overall "tariff" for each patient using a lookup table to assign a value according to the score the patient has given to each question. 
 Table 2: The ICECAP-A look-up table (Flynn, 2013)

1. Feeling settled and secu	re	
Level 4	0.222	
Level 3	0.191	
Level 2	0.101	
Level 1	-0.001	
2. Love, friendship and sup	oport	
Level 4	0.228	
Level 3	0.189	
Level 2	0.096	
Level 1	-0.024	
3. Being independent		
Level 4	0.188	
Level 3	0.156	
Level 2	0.084	
Level 1	0.006	
4. Achievement and progre	ess	
Level 4	0.181	
Level 3	0.159	
Level 2	0.091	
Level 1	0.021	
5. Enjoyment and pleasure		
Level 4	0.181	
Level 3	0.154	
Level 2	0.069	
Level 1	-0.003	

To calculate the overall tariff for a patient, the values next to their five scores in the look-up table are simply summed. For example, the tariff for a patient scoring 43211 would be calculated as follows:

0.222 + 0.189 + 0.084 + 0.021 - 0.003 = 0.513

ICECAP-A tariffs can range from zero to one (*note there is a small degree of rounding error in the look-up values provided, which may result in small deviations to this range*).

Either the overall tariff or the raw categories may be used in the statistical analyses, depending on the intended purpose of each individual analysis.

#### 9.2.5 HLQ scores

The Health Literacy Questionnaire comprises 9 scales. Unlike the other questionnaires in this study, the HLQ does not provide a single overall score. Instead, it provides means and standard deviations for each of the nine HLQ scales that indicate a person's strengths and needs in relation to their health literacy.

The Excel file (Q:\IPCAS\Documents\CRF\Information for Statistician\HLQ\HLQ Data Entry and Scoring\HLQ Scoring Using Excel.xlsx) contains information about the scales, instructions for scoring and how to handle missing data.

#### 9.2.6 SSMQ total score

The scale consists of 28 items that measure an individuals' self-management competency following stroke. Higher summed scores from the scale equate to someone with better self-management competency following stroke (Boger *et al*, 2015).

Each item is rated on a six-point response scale anchored by the responses 'Always True' and 'Always False'. Responses are allocated scores as follows:

Always true = 6 Mostly true = 5 Somewhat true = 4 Somewhat false = 3 Mostly false = 2 Always false = 1

Table 3: 15 items that are reverse scored (where 1=6, 2=5, 3=4, 4=3, 5=2, 6=1, shaded)

1	The effects of stroke mean that I cannot manage my recovery and health		
2	When things do not go well with my stroke, it is hard to stay positive		
3	It is not up to me to decide the best ways to manage my stroke		
4	The physical effects of stroke mean that I cannot manage my health		
5	It is hard to be motivated to seek out solutions to problems relating to stroke		
6	I am not sure what signs or symptoms mean my health is changing		
7	My problems with communication mean that I cannot manage my health		
8	My condition would improve if I received more professional help		
9	Whatever I do, I will not improve my condition		
10	The effects I take to manage my health have a positive effect		
11	I find it difficult to tell health professionals what I want or need		
12	I work out ways of managing my health together with health care professionals		
13	I am confident that health care professionals can answer my questions		
14	I feel confident at discussing any advice I don't understand with Doctors		
15	I feel confident at getting the information I need from health care professionals		
16	I know how to get help if I am concerned about my condition		
17	I plan my day so I can get things done without being tired		
18	I feel confident asking family members to help me do things important to my health		
19	I manage things related to stroke as well as other people with stroke		
20	I try different ways of doing things until I find out what works for me		
21	Ideas and things that work for other people with stroke are helpful to my recovery		
22	I have useful information or advice to give to others regarding managing after stroke		
23	I feel comfortable asking friends to help me do things important to my health		
24	I am concerned that the things I do to manage stroke may cause harm if not guided by my		
	health care professionals		
25	I cannot alter what my health care professionals decide to do about my stroke		
26	Following advice from health care professionals is the only way I will manage stroke		
27	I always follow professional advice about my health, to the letter		
28	Constant professional advice would help me to manage stoke		

# 9.3 Demographic and Baseline Variables

The demographic variables include age at baseline, gender, ethnicity and time since last stroke:

- Baseline demographics for the ITT population by trial arm up to [date] (N=) (Table 3.1)
- Baseline demographics for the ITT population by gender up to [date] (N=) (Table 3.2)

Questionnaire data will also be collected at baseline for SIS (short-form and full-form), EQ-5D-5L and ICECAP-A. A breakdown of the frequency of responses per level for each item of SIS domains 3 (emotion) and 8 (handicap) will be reported, as well as summary statistics for SIS domain 3 (emotion) and 8 (handicap), SIS-SF derived total score, EQ-5D-5L derived total score, and ICECAP-A derived total score. These summary statistics will be reported by treatment arm and gender (Tables 5.1-5.10).

# 9.4 Treatment Compliance

Treatment compliance is difficult to assess in the IPCAS trial as not all components of the intervention package are mandatory. Data on the delivery and uptake of the intervention components will be collected by the trial team with the intention of being able to demonstrate intervention fidelity (see Section 10.2.1 for details).

# **10** Efficacy and Fidelity Analyses

All efficacy variables will be summarised overall and by trial arm and gender at baseline and follow-up. N, mean, median, standard deviation, IQR will be used to summarise continuous efficacy variables, whereas number and percent will summarise categorical efficacy variables, as described in Section 9. Variables will not be summarised by cluster.

# **10.1 Primary Efficacy Analyses**

The standardised domain total scores will be calculated (as described in section 9.2.1) for each of the two co-primary outcomes (SIS emotional domain and SIS handicap domain). The analyses will focus on the evidence for a difference in SIS score (handicap or emotion) between the intervention and control group.

Each domain will be modelled separately and the following model fitted:

$$Y_i = \beta_0 X_{0i} + \beta_1 X_{1i} + \epsilon_i$$

For each co-primary outcome there is the potential for clustering and therefore a mixed effect model will be fitted with a random effect for general practice and fixed effects for the treatment group to assess the effect of clustering:

$$Y_{ij} = \beta_0 X_{0ij} + \beta_1 X_{1ij} + u_j + \epsilon_{ij}$$

Where,

Yij = continuous outcome SIS score (emotion/ handicap domain)

*i* = individual patient

j = cluster/ practice

 $X_1$  = dummy variable for the intervention treatment group.

X0 = baseline covariates (baseline score, gender, cluster size, time since last stroke at consent)

 $\beta_0$  = intercept which represents the population average SIS score

 $\beta_1$  = difference in score between intervention and control groups at 12 months

 $u_i \sim N_1(0, \sigma_h^2)$  is the cluster-level random practice effect

 $\epsilon_{ii} \sim N_1(0, \sigma_e^2)$  is the residual error

There is an a priori hypothesis that the following covariates may be associated with the co-primary outcomes: gender, age at baseline (categorical), time since last stroke (categorical), general practice list size (the stratifying variable used in the randomisation, split into two categories; <10,500 and  $\geq$ 10,500 patients) and deprivation score (continuous, both at the patient and practice level). Once the primary analysis model is decided, these covariates will be added to assess and changes in treatment effect on the co-primary outcomes.

Each data point will be assumed to have an error term that is identically and independently normally distributed with constant variance. These assumptions will be checked using histograms and box plots to look at the distributional form of the primary outcome SIS scores. All assumptions for the linear mixed effects models will be assessed by viewing plots of the residual values and QQ plots. If any of the assumptions of the linear mixed model are violated then the dependent variable, SIS score, may be transformed to normality or if this fails to correct the distributional assumptions, non-Gaussian or semi/non-parametric methods for analysis will be used.

 $Y_{ijk} = \beta_0 X_{0ij} + \beta_1 X_{1ij6} + \beta_2 X_{1ij12} + u_j + \varepsilon_{ijk}$ 

The analysis population for the primary outcome will be all patients with 12-month outcome measure as the mixed effects model assumes missing at random (MAR).

For missing data analysis the following model will be fitted if there is a cluster effect:

Yijk = continuous outcome SIS score (emotion/ handicap domain)

*i* = individual patient

j = cluster/ practice

*k* = 6 month and 12 follow-up scores

 $X_1$  = dummy variable for the intervention treatment group.

X0 = baseline covariates (baseline score, gender, cluster size, time since last stroke at consent)

 $\beta_0$  = intercept which represents the average baseline SIS score for person *i* 

 $\beta_1$  = difference in score between intervention and control groups at 6 months

 $\beta_2$  = difference in score between intervention and control groups at 12 months (primary)

 $u_i \sim N_1(0, \sigma_b^2)$  is the cluster-level random practice effect

$$\begin{pmatrix} Y_{ij0} \\ Y_{ij6} \\ Y_{ij12} \end{pmatrix} \sim MuN \begin{pmatrix} \beta_0 \\ \beta_0 + \beta_1 + X_{ij6} \\ \beta_0 + \beta_2 + X_{ij12} \end{pmatrix}$$

$$\epsilon_{ijk} \sim MuN \begin{pmatrix} 0 \\ 0, \Sigma_0 \\ 0 \end{pmatrix}$$
 is the residual error, and  $\Sigma_0$  initially has an AR1 structure.

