10.2. Analysis of Primary Outcome

We will use intention to treat (ITT) methods for the analysis of the primary end-points. A mixed effects model will be used to model each of the co-primary outcomes with a cluster random effect and fixed effects for the intervention and covariates that might potentially confound the relationship. Distributional assumptions will be assessed graphically by residual q-q plots and residual by fitted value plots. To handle the co-primary outcomes, 97.5% confidence intervals will be reported for the two primary treatment effects which are equivalent to having the Bonferonni correction on the planned 5% significance level for a single endpoint.

The missing data will be analysed under the assumptions of missing completely at random and missing at random. Multiple imputation will be used to impute missing outcome data and the various potential predictors of missingness will be included in the imputation model. Additionally, a sensitivity analysis may be used to investigate non-ignorable missingness mechanisms and their influence on the results.

The full details of the statistical analysis will be specified in the statistical analysis plan (SAP).

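### SAP 10.1 lets the co-primary analysis move to an unnamed transformation or method after a visual check, so the treatment effect may no longer be a difference in SIS points

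*SAP*

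**What the plan says.** SAP 10.1 fits a mixed model to each SIS domain separately, with a random practice effect. The treatment coefficient is defined as the "difference in score between intervention and control groups at 12 months". SAP 9.2.1 puts each domain score on a 0-100 scale; the emotion domain has nine items scored 1 to 5.

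The assumption checks come in two sentences. The first looks at the outcome itself: "These assumptions will be checked using histograms and box plots to look at the distributional form of the primary outcome SIS scores". The second looks at the fitted model: "All assumptions for the linear mixed effects models will be assessed by viewing plots of the residual values and QQ plots". The consequence follows: "If any of the assumptions of the linear mixed model are violated then the dependent variable, SIS score, may be transformed to normality", and if this does not correct the distribution, "non-Gaussian or semi/non-parametric methods for analysis will be used".

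The same section treats the primary model as still to be settled: "Once the primary analysis model is decided, these covariates will be added".

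Protocol 10.2 has only a routine diagnostic ("Distributional assumptions will be assessed graphically by residual q-q plots and residual by fitted value plots"). It has no switching rule and leaves detail to the SAP.

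**The concern.** A bounded sum of five-point items is likely to show skew, a ceiling or unequal variance, so the fallback may well be invoked. If it is, the SAP does not say which transformation, which alternative method, how bad a plot must look, who judges it, or how the result returns to SIS points. Residual plots need a fitted model, so a treatment estimate already exists when the choice is made. The trial is open-label with subjective co-primaries (SAP 6.3), and the statistician holds the randomisation lists (SAP 6.4).

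At stake is what the primary result means. A reader expects a difference in points on a 0-100 scale with a 97.5% confidence interval. The plan allows a coefficient on another scale, or a rank result, for one domain or both. The COVID-19 analysis in SAP 12 repeats the primary analysis and would inherit the switch.

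**Working it through.** **1. The plan's own figure.** From SAP 7: 23 practices per arm, 20 patients each, ICC 0.03, CV of cluster size 0.65, 20% loss, effect size 0.33, 2.5% significance (taken as two-sided, in line with the 97.5% intervals).

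- Design effect = 1 + ((CV² + 1)m − 1) × ICC; effective n per arm = 23m / design effect; power = Φ(0.33 × √(n/2) − 2.241).
- m = 20 × 0.8 = 16: design effect 1 + (1.4225 × 16 − 1) × 0.03 = 1.653; n = 368/1.653 = 222.7; power = Φ(3.482 − 2.241) = 89.3%.
- m = 20: design effect 1.8235; n = 460/1.8235 = 252.3; power = Φ(3.706 − 2.241) = 92.9%.

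This agrees with the stated figure of at least 90% to within a point. The effect size is standardised; neither document gives an SD or a difference in points.

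**2. The decision path.**

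| Step | Specified | Not specified |
|---|---|---|
| Check | Histograms, box plots, residual and QQ plots | Threshold; who judges; blinding to arm |
| First fallback | Transform towards normality (permissive) | Which transformation; back-transformation |
| Second fallback | A class of methods | Which method; what it estimates |
| Reporting | Mixed-model coefficients, 97.5% intervals | Counterpart after a switch; retention of the untransformed result |

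**3. What a transformation does to the scale.** Take squaring, (score/100)² × 100, as an example; the SAP names none. The emotion domain has a raw range of 36, so one raw point is always 100/36 = 2.78 SIS points. After squaring, the lowest step is worth 100 × 1²/36² = 0.08 and the highest 100 × (36² − 35²)/36² = 5.48, a ratio of 71. A difference in squared scores therefore has no fixed equivalent in SIS points, and a rank result has none either.

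**4. Type I error at nominal 2.5%.** All runs use 46 practices, a mean of 16 analysed (46 × 16 = 736 patients), CV 0.65 and ICC 0.03. The score distributions are assumptions; the documents give none.

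| Assumed distribution | Untransformed | Transformed | Rank | Residual-triggered switch | Best of three |
|---|---|---|---|---|---|
| A: 33% at ceiling, skew −1.0 | 2.66% | 2.76% (log-reflected) | 2.66% | not run | 3.82% |
| B: mean 72, SD 22, baseline correlation 0.6, capped at 100 | 2.62% | 2.55% (squared) | 2.65% | 2.46% | 3.20% |
| C1: about 35% at ceiling, skew −1.1 | – | – | – | 2.3–2.5% | 3.6% |
| C2: about 11% at ceiling | 2.9% | – | – | 2.9% | 4.1% |

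A used 5,000 trials with REML random-intercept fits and 44 df. B (8,000 trials) and C (5,000 each) used a weighted practice-level stand-in for the mixed model. In B the switch goes only to the squared score; in C it follows the SAP's ordered path. Monte Carlo error is √(0.025 × 0.975/8,000) = 0.17 points for B and 0.22 for 5,000 trials. A dash means no figure is available.

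**5. How often the fallback would fire.** In B, a formal residual normality test triggered a switch in 84% of null trials and 96% of trials with an effect. With about 11% at ceiling, a trigger of absolute residual skew above 0.5 fired in only 8%. Use of the fallback therefore depends on the threshold, which the SAP leaves to the eye.

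**6. Power.** In B at 0.33 SD: untransformed 94.9%, squared 94.7%, rank 94.6%. These exceed the 89.3% in step 1 because the simulation adjusts for baseline.

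**The case against.** The strongest defence is that the rule is ordered and driven by diagnostics: untransformed first, then a transformation, then another method only if that fails. It does not invite running several analyses and reporting the most favourable. A reader might infer from the 3.2–3.8% figures that the SAP's rule inflates type I error. It does not: those figures describe picking the smallest of three p-values, which would depart from the plan. The switch itself shows no detectable inflation. This part of the defence stands.

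Three other strong readings also fail. A reader might say the trial was sized on a difference in SIS points; it was sized on a standardised 0.33, so the scale argument rests on the definition of the treatment coefficient. A reader might call a switch nearly certain; it is likely, but step 5 shows how far that turns on the threshold. And Protocol 10.2 is an ordinary residual check, not a second instance of the problem.

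The outcome histograms ("checked using histograms and box plots to look at the distributional form of the primary outcome SIS scores") are a minor matter, because the residual checks follow in the next sentence.

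Safeguards exist: hard-locked data and an approved SAP before the final analysis (SAP 8.1), and no efficacy analyses for monitoring (SAP 8.4.2). They limit early looks but do not settle the method, because the approved SAP itself leaves it open. SAP 10.1 also expects results from linear mixed models, but does not say what replaces them after a switch.

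**Conclusion.** The concern holds as an under-specified fallback whose main cost is the effect scale. If it is invoked, the primary result may have no stated meaning in SIS points, the co-primaries may be on different scales, and the untransformed estimate need not be reported. This follows from the text and needs no distributional assumption.

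The type I error risk is secondary: about 2.5% under a purely residual-triggered switch (2.9% in one scenario, where the untransformed model was also at 2.9%). The worst case of free choice is about 3.2–3.8% per co-primary, with 4.1% in that same scenario. The untransformed model rejected 2.6–2.7% in runs A and B, so under those assumed distributions a switch is not needed for validity. The simulations show direction and rough size only. The point merits a change before analysis but does not undermine the design.

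**What to change.** In SAP 10.1, state that the linear mixed model on the untransformed 0-100 score is the primary analysis for both domains, whatever the residual plots show. Replace the transform-or-switch rule with a pre-named sensitivity analysis on the same scale if the plots are poor, for example cluster-robust standard errors or a practice-level cluster bootstrap. Any transformed or rank analysis should be a sensitivity analysis only. Reword the sentence that speaks of deciding the primary model, so that it reads as already fixed. Removing the outcome histograms from the assumption check is optional.

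Naming the transformation, the order and the back-transformation in advance would also remove the discretion, but it keeps the scale problem unless the result is returned to SIS points.

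Cost: a few lines of SAP text and at most one extra run per domain. Sample size and the 2.5% level do not change. The downside is a small loss of efficiency if the distribution is extreme; under scenario B there was none (94.9% untransformed, 94.6% rank).
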